**Protocol-specified exempt events (protocol section 10.2.5)**

The following events are protocol-specified exempt events. They are **not** reported as AEs or SAEs, **unless** the investigator considered that there was a reasonable possibility that the study intervention (blinded investigational agent/ placebo or study-supplied SOC treatment) caused the event.

- Death
- Stroke
- Meningitis
- Encephalitis
- Myelitis
- Myocardial infarction
- Myocarditis
- Pericarditis
- New onset of worsening of CHF (NYHA class 3 or 4)
- Arterial or deep vein thromboembolic events
- Respiratory failure defined as receipt of high flow nasal oxygen, non-invasive ventilation, invasive mechanical ventilation or ECMO
- Hypotension requiring vasopressor therapy
- Renal dysfunction requiring renal replacement therapy
- Hepatic decompensation
- Neurologic dysfunction, including acute delirium and transient ischemic events
- Disseminated intravascular coagulation
- Major bleeding events
- Serious infections

## Appendix D. Schedule of Assessments

**Table D-1. Schedule of Assessments (protocol version 5.1, Appendix B).\***

	Screen or Day 0	Day 0	Follow-up Study Day; shaded columns denote in-person visits															
Day	-1/0 	0	1	2	3	4	5	6	7	14	28	42	60	75	90	6M	12M	18M
Acceptable deviation from day	0	0	0	0	0	0	0	0	+1	+2	+3	+3	+5	+5	+10	±14	±14	±14
ELIGIBILITY & BASELINE DATA																		
Informed consent	X																	
Baseline medical (incl. duration of COVID-19) and social history	X																	
Baseline medications	X																	
Symptom-directed physical exam by the clinical team	X																	
Review SARS-CoV-2 test results	X																	
Local laboratory testing	X							X										
Urine pregnancy test or other documentation of pregnancy status	X																	
STUDY INTERVENTION																		
Randomization		X																
Study Drug/Placebo Administration		X																
Assess infusion completion and adverse reactions		X																
STUDY PROCEDURES																		
Clinical assessment for pulmonary ordinal outcome	X	X	X	X	X	X	X	X	X	X	X							
Clinical assessment for pulmonary+ ordinal outcome	X	X	X	X	X	X	X	X	X									
Vital signs for NEW score assessment	X																	
Respiratory function scale assessment	X																	
Hospitalization status				X		X		X	X	X		X		X	X	X	X	X
Changes in residence/facility											X	X	X	X	X	X		
Interim medical history									X	X	X		X		X			
Interim medications						X				X								
Clinical AEs of any grade on days indicated		X	X	X	X	X	X	X	X	X	X							
Clinical AEs reaching grade 3 or 4 severity through Day 28										X	X							
Research sample storage (plasma and serum) 		X	X		X		X				X				X			
Midturbinate swab for central SARS-CoV-2 viral load testing 		X																
SAEs and unanticipated problems																		
Deaths																		
Hospitalization Summary																		
Hospital Readmissions																		

 Screening must be performed within 24 hours of randomization.

 Blood draw and swab collection in some cases can be obtained after randomization but before the infusion. If it is not possible to do an in-person on Day 3 or Day 5, the blood draws may be done one day earlier or one day later (but the participant should be telephoned to record the clinical data on the indicated study day).

\* In addition, in protocol versions 3.0 and higher, pregnancy outcomes will be collected for female participants who become pregnant during the study.

## Appendix E. Modifications to the Statistical Analysis Plan for AZD7442

### Investigational Agent

Appendix H4 (version 2 dated 09 April 2021) of the TICO protocol describes agent-specific protocol elements for AZD7442 by AstraZeneca. AZD7442 is comprised of two immunoglobulin G (IgG)-1 kappa monoclonal antibodies (AZD8895 and AZD1061) which neutralize SARS-CoV-2 by binding to unique, non-overlapping epitopes on the RBD of the viral spike protein.

### E-1 Analysis population

Treatment comparisons for **efficacy and safety** outcomes will be by modified intention-to-treat (mITT). The mITT analysis is restricted to participants who received a complete or partial infusion of the investigational agent/placebo; participants who did not receive any of the investigational agent/placebo are excluded. The TICO platform protocol specifies ITT for the efficacy analyses “unless otherwise stated”, and mITT for safety analyses.

*Justification for changing the study population to mITT for efficacy analyses:* In the TICO trial of AZD7442, 1455 patients were randomized (ITT population). In preliminary, near final data, of the 1455 randomized participants, 1417 were infused the blinded AZD7442 or placebo. Of the remaining 38 participants, 35 had withdrawn consent prior to infusion (no follow-up data after Day 0 were collected for 34 of the 35), and information was pending on 3 participants as of December 28, 2021. Because the treatment assignment was blinded, the reasons for not receiving an infusion are independent from the treatment assignment. Therefore, the risk of bias due to restricting analyses to the mITT cohort is low. Moreover, follow-up data are not available for most of the participants who did not receive an infusion. With this approach, the risk and benefits of AZD7442 will be evaluated in the same population.

**Comment:** Investigators were unblinded to summaries of the infusion status of participants, pooled across treatment groups. These analyses were included in the open DSMB reports.

### E-2 Increase in Target Number of Primary Events and Sample Size Beyond That Specified in the Master Protocol

The event target and sample size for AZD7442 was increased on August 19, 2021 with a letter of amendment. This increase was based on the results of other trials (the RECOVERY trial and the ACTIV-3/TICO trials of bamlanivimab, VIR-7831 and BRII-196/198) and utilized pooled outcome data for AZD7442 to estimate the revised sample size. The new event target for the AZD7442 trial was 1,228. It was estimated that extending enrolment to September 30, 2021 would achieve a sample size of 1,500 participants, which was estimated to be required to achieve the event target of 1,228. With this event target a RRR of 1.20 could be detected with 90% power at the 0.05 (2-sided) level of significance. It also provided 90% power to detect a RRR of 1.28 for the subgroup of participants who are seronegative for neutralizing SARS-CoV-2 antibodies (nAb) at study entry (see Letter of Amendment of 19 August 2021).

### E-3 Power Estimation Prior to Unblinding

On December 28, 2021, prior to unblinding any treatment comparisons for the trial of AZD7442, power was re-assessed based on updated pooled (AZD7442 and placebo groups combined) primary endpoint results. Pooled primary outcome data on December 28, 2021 are given in the table below.

**Table E-1.** Recovery status of participants in the AZD7442 trial as of December 28, 2021

	1455 Participants Randomized				
	1417 Infused and 38 not infused (35 withdrew consent)				
	nAb negative	nAb positive	Specimen not yet analyzed	Specimen not available	TOTAL
Recovery status through Day 90	N=616	N=657	N=107	N=37	N=1417
Withdrew prior to recovery	2	4	0	0	6
Day 90 window closed and recovery status unknown	17	5	0	1	23
Day 90 window not yet closed* and recovery status unknown	0	1	3	0	4
Achieved sustained recovery	508	586	76	25	1195
Home < 14 days	7	5	0	0	12
Discharged from hospital, but not home	9	3	0	2	14
Hospitalized	12	10	2	1	25
Died before recovery	61	43	26	8	138

\* The Day 90 window extends to Day 100.

The mITT study population included 1417 participants. At this time, most of the 90-day follow-up was completed. The last patient was randomized on September 30, 2021 and the visit window for the Day 90 visit extends to 100 days (January 8, 2022).

Overall, the number of primary events was 1,195, 33 events less than the target of 1,228. As the table below indicates, this does not have a material effect on power.

**Table E-2.** Power estimates in the full study population: Recovery rate ratios (RRR) that can be detected with 80-90% power and 0.05 (2-sided) significance level, assuming 1195 sustained recovery events pooled across treatment groups

Power	RRR
0.90	1.206
0.85	1.189
0.80	1.176

**Table E-3** below summarizes power estimates for the subgroup of participants who were nAb-negative at study entry. This subgroup is currently 48% of those for whom the baseline nAb status was determined. We anticipate results for 107 additional patients in January 2022. The effect sizes (recovery rate ratio [RRR]) that can be detected with 90%, 85%, and 80% power for different estimates of the final number of primary events for the nAb-negative subgroup are summarized below; as of December 28, 2021, 508 participants in this subgroup had achieved sustained recovery, and 76 participants among those for whom the nAb status is not yet known.

**Table E-3.** Power estimates in the nAb negative subgroup: RRRs that can be detected with 80-90% power and 0.05 (2-sided) significance level, assuming 542-562 sustained recovery events

Power	RRR (542 events)	RRR (552 events)	RRR (562 events)
0.90	1.321	1.318	1.315
0.85	1.294	1.291	1.288
0.80	1.272	1.269	1.267

In preliminary data in August 2021, 56% of participants were nAb-negative. With the more complete baseline data on December 28, 2021, this percentage is estimated as 48%.

The power estimates given in [Tables E-2](#) and [E-3](#), the decline in the estimated percentage of participants who were nAb-negative, and further consideration of the relative importance of the treatment comparisons in the full study cohort as well as the in the nAb-negative subgroup led to the plan to test both hypotheses (benefit of AZD7442 in the full study population, and benefit of AZD7442 in the subgroup of nAb-negative participants) simultaneously while controlling the family-wise type 1 error rate. This is described in section [E-4](#) below.

## **E-4 Primary Analysis: Simultaneous Tests in the Overall Cohort and in the nAb-Negative Subgroup, Method and Power Considerations**

*Primary analysis:* Two hypotheses will be tested using mITT analyses. The family-wise type 1 error rate will be controlled at the 0.05 (2-sided) level of significance. The two primary comparisons are:

- AZD7442 versus placebo for time to sustained recovery in the overall mITT cohort; and
- AZD7442 versus placebo for time to sustained recovery in the subgroup of participants in the mITT cohort who were nAb-negative at study entry.

The Holm method will be used to control the family-wise error rate. With this approach, the two primary comparisons are considered on an equal footing (i.e., co-primary hypotheses). With the Holm method, p-values for the 2 hypotheses will be ordered from lowest to highest. The lower of the two p-values will be compared with a 0.025 (0.05/2) 2-sided level of significance. If that test result is significant (i.e.,  $p \leq 0.025$ ), the second p-value will be compared with a 0.05 (2-sided) level of significance. This method controls the family-wise type 1 error rate for both comparisons at 0.05 (2-sided).

Power was estimated considering the estimated number of participants with a primary endpoint of sustained recovery for the nAb negative and positive subgroups. Based on the results of recently reported trials mentioned in section [E-2](#), we expect the recovery rate ratio (RRR) for AZD7442 versus placebo to be greater (more favorable for AZD7442 than placebo) for the nAb-negative subgroup than for the nAb-positive subgroup.

The following assumptions were made for the power estimates given in the figure and table below; projections for event numbers are based on [Table E-1](#):

- Sustained recovery by Day 90 will be experienced by an estimated 545 participants in the nAb-negative subgroup. This projection includes the 508 participants who have had experienced the endpoint by December 28, 2021, and 37 additional participants who

experienced a sustained recovery endpoint (either nAb negative participants with unknown recovery status or participants for whom nAb status at baseline had not yet been determined on December 28, 2021).

- In the overall cohort, 1202 participants will achieve sustained recovery; this projection includes the 1195 participants who had achieved sustained recovery as of December 28, 2021, plus a small proportion of participants with as yet unknown outcome status.
- 48% of the study participants would be nAb-negative at study entry

With 545 primary events in the nAb-negative subgroup, power is 0.90 to detect a RRR=1.32 at the 0.05 (2-sided) level of significance. With the above assumptions, and assuming RRR=1.32 for the nAb-negative subgroup, power for the comparison of AZD7442 and placebo in the overall cohort and within the nAb-negative subgroup was estimated for a range of values of the RRR for the nAb-positive subgroup. In [Table E-4](#) below, the first column shows the assumed RRR among the nAb-positive subgroup, the second column shows the corresponding overall RRR (assuming RRR=1.32 among the nAb-negative subgroup), and columns 3 and 4 show the estimated power to detect RRR=1.32 among the nAb-negative subgroup and the computed RRR (column 2) in the overall study cohort, respectively, using Holm's method to control the simultaneous Type 1 error to 0.05. For example, assuming RRR=1.0 among the nAb-positive subgroup and RRR=1.32 among the nAb-negative subgroup, the overall RRR would be 1.14, and the treatment difference between AZD7442 and placebo would be detected with power of 0.858 in the nAb-negative subgroup, and with power of 0.63 in the overall study population.

**Comment:** In a single test with 5% significance level, power was estimated at 90% to detect RRR=1.32 in the nAb-negative subgroup; assuming RRR=1.14 in the full study cohort, the power in the nAb-negative subgroup is decreased to 86% with Holm's procedure because the p-value for the nAb-negative subgroup would more likely be the smaller of the two p-values, and thus would be compared to 0.025 instead of 0.05.

**Table E-4.** Power to detect a treatment difference in sustained recovery between AZD7442 and placebo within the nAb-negative subgroup and overall, assuming an RRR of 1.32 among the nAb-negative subgroup and a range of RRRs between 1.30 and 0.95 for the nAb-positive subgroup, and using Holm's method to control the familywise Type 1 error.

[figure not shown]
Assumed RRR		Power using Holm's method	
Among the nAb-positive subgroup	Overall*	To detect RRR=1.32 among the nAb-negative subgroup	To detect the overall RRR (column 2)
1.30	1.31	0.900	0.994
1.25	1.28	0.899	0.985
1.20	1.26	0.897	0.967
1.15	1.23	0.892	0.933
1.10	1.20	0.884	0.873
1.05	1.17	0.871	0.774
1.00	1.14	0.858	0.630
0.95	1.11	0.848	0.453

\* RRR for sustained recovery in the overall study population, assuming RRR=1.32 among the nAb-negative subgroup and the RRR in column 1 among the nAb-positive subgroup

[Figure E-1](#) below shows the data from [Table E-4](#) in a graph. The power of Holm's testing procedure to detect a treatment effect is plotted versus a range of assumed RRRs among the nAb-positive participants (horizontal axis, column 1 of [Table E-4](#)); the dashed line shows the

power to detect  $RRR=1.32$  for the nAb-negative subgroup (column 3 in [Table E-4](#)), and the solid line shows the power to detect the corresponding treatment effect in the overall cohort (column 4 in [Table E-4](#)).

**Figure E-1.** Estimated power to detect a treatment difference in sustained recovery between AZD7442 and placebo in the overall study population (solid line) and within the subgroup of nAb-negative participants (dashed line), for a range of RRRs among nAb-positive participants and assuming  $RRR=1.32$  for nAb-negative participants.

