### Censoring for time-to-event analyses

For **interim** analyses, the type of censoring used will depend on the data collection schedule.

- If the reporting of the endpoint is data-driven (e.g., SAEs and deaths are reported as they occur), then follow-up is censored at the administrative censoring date, at the date of withdrawal, or loss to follow-up, whichever occurs earliest.
- If the date of the event is elicited retrospectively at fixed study visits spaced more than one week apart (e.g., “sustained recovery”), follow-up will be censored at the last day the endpoint status was ascertained.
- Sensitivity analyses will be provided for key analyses when the outcome status is uncertain.

For **final** analyses, follow-up will be censored on the last day the outcome status was ascertained.

**Adverse events** (AEs) will be classified by system organ class according to MedDRA® (currently version 24.1 [September 2021] is used; when new versions are implemented, items are recoded). AEs will be graded according to the *DAIDS Table for Grading the Severity of Adult and Pediatric Adverse Events, Corrected Version 2.1* (July 2017) (also referred to as the *DAIDS AE Grading Table*). Cause of death will also be coded according to MedDRA®.

The number and percent of participants with grade 1-4 AEs will be summarized by day and grade, and by MedDRA® System Organ Class and grade. The percentage of participants with AEs will be compared between treatment groups according to grade cut-offs, e.g., “percent of participants with any AE”, “percent of participants with grade 2 or higher AEs”, etc., using CMH tests. The total number of events and median (IQR) of events per participant will also be summarized.

Additionally, the incidence of grade 3 and higher AEs will be summarized (number and percent of participants), and compared between treatment groups using time-to-event methods.

**Significance level, two-sided tests:** Unless noted otherwise, statistical tests and confidence intervals will be 2-sided, confidence intervals will have approximate 95% coverage probability, and test results with P-values  $\leq 0.05$  will be considered “significant”. Percentages will be reported to at least one decimal place. P-values will be given to 2 significant figures.

**Cut-date for interim reviews:** Analysis data sets will be frozen (locked) several days (or weeks) prior to the review date, to allow the unblinded statisticians time to prepare a consistent

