## 10.3 Interim Monitoring Guidelines for the Primary Endpoint

This section describes the interim monitoring guidelines that apply after the investigational agent has passed the initial futility assessment (after approximately 150 participants per study arm are enrolled).

As a guideline, asymmetric boundaries will be provided to monitor the primary endpoint (time to sustained recovery) for overwhelming benefit or for harm. The trial of an investigational agent should be stopped for efficacy only if there is clear and convincing evidence of superiority

of the agent versus the pooled control group with respect to the primary outcome, time to sustained recovery. For monitoring superiority, the Lan-DeMets spending function analogue of the O'Brien-Fleming boundaries will be used, with a 1-sided 0.025 level of significance over multiple looks. For computing the Lan-DeMets boundary, the information fraction at each interim analysis will be the observed total number of sustained recoveries divided by the planned number of sustained recoveries (N=843).

The monitoring boundary for harm is asymmetric, requiring less evidence to stop for harm than for superiority; a Haybittle-Peto boundary with 2.5 SD for the first 50 participants enrolled and 2.0 SD afterwards will be used as a guideline for harm. With this approach, less evidence will be required for crossing a boundary for harm than for benefit.

At each full interim review after the first 169 participants have achieved sustained recovery (20% information time), the following will be provided:

- Signed square root of the value of the test statistic for Gray's test with  $\rho=0$ , ("Z-value") comparing the investigational agent versus the control group for the primary endpoint through Day 90, plotted over information time, and the asymmetric monitoring boundaries: the O'Brien-Fleming boundary with Lan-DeMets  $\alpha$ -spending function for superiority (one-sided test with  $\alpha=0.025$ ), and the asymmetric, Haybittle-Peto boundary for harm described above.
  - **Comment:** Test statistics for the primary treatment comparison will be coded such that the value of the test statistic  $> 0$  favors the investigational agent. Thus, in case of harm, the Haybittle-Peto boundary with 2 SD of the normalized test statistic, is crossed if the Z-value for the test statistic is below -2, irrespective of information time.

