## E-6 Interim Monitoring Guidelines

There are 2 changes to the interim monitoring guidelines described in Section 10.3 of this SAP:

- The information fraction for the Lan-DeMets spending function will be based on the target of 1,228 sustained recoveries, not 843.
- As part of the broad assessment of risk/benefit, the DSMB should consider the findings in nAb negative and nAb positive subgroups. For participants who are nAb negative, greater benefit with the investigational agent is hypothesized.

**Comment:** The antibody status at baseline was unknown for a large proportion of participants until late in the trial. Therefore, separate interim monitoring boundaries were not planned for this subgroup.

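### For AZD7442, E-4 claims family-wise control from Holm's final thresholds without allowing for the efficacy looks that section 10.3 and E-6 keep on the overall hypothesis

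*SAP*

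**What the plan says.** SAP E-4 sets two co-primary hypotheses for AZD7442: benefit in the overall mITT cohort and benefit in its nAb-negative subgroup. "The family-wise type 1 error rate will be controlled at the 0.05 (2-sided) level of significance". For Holm's first step, "The lower of the two p-values will be compared with a 0.025 (0.05/2) 2-sided level of significance". If that test succeeds, "the second p-value will be compared with a 0.05 (2-sided) level of significance". E-4 then states: "This method controls the family-wise type 1 error rate for both comparisons at 0.05 (2-sided").

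Section 10.3 monitors the primary endpoint for superiority with the Lan-DeMets analogue of the O'Brien-Fleming boundary, "with a 1-sided 0.025 level of significance over multiple looks". On timing it says: "At each full interim review after the first 169 participants have achieved sustained recovery (20% information time), the following will be provided".

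E-6 makes two changes to section 10.3 for AZD7442. The first concerns the event target: "The information fraction for the Lan-DeMets spending function will be based on the target of 1,228 sustained recoveries". The second asks the DSMB to weigh the findings by nAb status. E-6 adds that no separate boundary was planned for the nAb-negative subgroup. The efficacy boundary on the overall comparison therefore remains. Neither E-4 nor E-5 refers to it.

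**The concern.** Holm controls the family-wise error when each p-value it receives is valid at the level used. The overall-cohort p-value is not valid at 0.025 or 0.05 if the same hypothesis could already have been rejected at an interim look. The interim boundary can use the whole one-sided 0.025, and the final test then uses its full Holm level again. The subgroup test has no looks, so it is unaffected.

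At stake is the property E-4 was written to secure. The exposed result is a marginal one in the overall cohort. Once the subgroup has been rejected, a two-sided overall p-value between about 0.044 and 0.05 would be declared significant although alpha spent at the looks no longer supports it (figures for looks at 50% and 75%).

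**Working it through.** **Inputs.** E-4 projects 545 events in the nAb-negative subgroup and 1,202 overall. The final test statistics then have correlation √(545/1202) = 0.673. Allocation is 1:1 (section 1.3). Holm's critical values are 2.241 (two-sided 0.025) and 1.960 (two-sided 0.05). Look times are an assumption: 50% and 75% information, the only later review times the SAP names, and it names them for futility (sections 2 and 10.4).

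**Step 1: the plan's own figures.** The RRR detectable with a given power is exp[2(z_crit + z_power)/√D].
- Table E-2 (D = 1,195, power 0.90, 0.85, 0.80): z_crit = 1.960 gives 1.206, 1.189 and 1.176, exactly as printed. z_crit = 2.014 (the adjusted value from step 2) would give 1.210, 1.193 and 1.180.
- 545 events at RRR 1.32: ln(1.32)·√545/2 = 3.241, so power = Φ(3.241 − 1.960) = 0.900, as stated.
- Table E-4: a bivariate normal with unadjusted 2.241/1.960 reproduces all 16 power cells within 0.01 (for example 0.851/0.623 against 0.858/0.630).

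The plan's power was therefore worked out for an unadjusted final test.

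**Step 2: boundaries.** Cumulative one-sided spending is α(t) = 2[1 − Φ(2.241/√t)].
- t = 0.50: 2[1 − Φ(3.170)] = 0.0015
- t = 0.75: 2[1 − Φ(2.588)] = 0.0097

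Solving by numerical integration gives Z boundaries of 2.963, 2.359 and 2.014 for one-sided 0.025. The final value corresponds to two-sided p = 0.0440. For one-sided 0.0125 (Holm's first step) they are 3.345, 2.670 and 2.281, the last being two-sided p = 0.0225.

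**Step 3: family-wise error.** In the simulation, an interim crossing rejects the overall null; otherwise Holm is applied exactly as E-4 states. The subgroup drift is ln(RRR)·√(545/4). Runs used 20 to 40 million trials per row (standard error at most about 0.00005). Each cell gives the benefit-direction rate, then the two-sided rate.

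| Truth | Holm, no looks | E-4 with looks at 50% and 75% |
|---|---|---|
| Both nulls true | 0.0218 / 0.0436 | 0.0258 / 0.0476 |
| Overall null, subgroup RRR 1.24 | 0.0248 / 0.0381 | 0.0275 / 0.0408 |
| Overall null, subgroup RRR 1.32 | 0.0250 / 0.0411 | 0.0276 / 0.0438 |
| Overall null, subgroup RRR 1.50 | 0.0250 / 0.0491 | 0.0277 / 0.0518 |
| Overall null, subgroup always rejected | 0.0250 / 0.0500 | 0.0277 / 0.0527 |

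The reference values are 0.025 and 0.05.

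**Step 4: other look schedules**, for the last row of the table:
- one look at 50%: 0.0255 / 0.0505
- one look at 75%: 0.0276 / 0.0526
- looks at 20, 40, 60 and 80%: 0.0283 / 0.0533
- looks at 25, 50, 75 and 90%: 0.0294 / 0.0544

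Under the global null, a single look at 50% leaves the benefit-direction rate at 0.0224, below 0.025. The four looks ending at 90% take the two-sided rate to 0.0512.

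**Step 5: the corrected final values.** The simulation was repeated with final overall values of 2.281 and 2.014, leaving the interim looks at the full-level boundary of section 10.3. The benefit-direction rate is 0.0251 under the global null and 0.0250 or less in the other rows after rounding. The two-sided rate is at most 0.047.

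**The case against.** The strongest reply is that E-4 claims a two-sided rate, and in the most plausible configurations that rate is not breached. The SAP reports bamlanivimab RRRs of 1.24 (nAb-negative) and 0.74 (nAb-positive), with 0.99 overall. A reader might infer that this pattern breaks the 0.05 claim. It does not: with a null overall effect and a subgroup RRR of 1.24, the two-sided rate is 0.041. Only the benefit-direction rate exceeds its share. This part of the reply stands.

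Three further points also stand.

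- A reader might infer that alpha has already been spent. No section says that an AZD7442 efficacy look took place, or when. Section 10.3 also presents its boundaries as guidelines to the DSMB.
- A reader might want the interim boundary reset to Holm's first-step level. E-3 dates the reassessment behind the Holm plan to 28 December 2021, after randomization had ended and with most 90-day follow-up complete, so this is largely moot. With looks at 50% and 75%, spending before the final test is 0.0097, inside Holm's one-sided 0.0125.
- A reader might extend the point to agents with one primary hypothesis through the p ≤ 0.05 default in section 3. That default opens "Unless noted otherwise, statistical tests and confidence intervals will be 2-sided", and section 10.3 does specify otherwise for the primary endpoint. At most this is a request for clearer wording.

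The reply does not rescue E-4's unqualified statement. Section 10.3 could be read as implying a reduced final critical value, but E-4 prints its own thresholds without referring to it, and Table E-2 matches only the unadjusted value.

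**Conclusion.** The point holds in a limited form. If efficacy looks on the overall hypothesis take place, Holm at 0.025/0.05 does not guarantee family-wise control in every configuration of true effects. With assumed looks at 50% and 75%, the benefit-direction error is 0.026 to 0.028 against 0.025. The two-sided rate passes 0.05 only for large subgroup effects, reaching about 0.052 to 0.053. With no efficacy look, E-4 is correct as written.

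These sizes assume the stated look times, E-4's projected event counts, non-binding futility rules, and a harm boundary that is not counted as a claim of benefit. The inflation is small, but it affects a property the SAP states outright, so E-4 should be corrected.

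**What to change.** In E-4, state that the final overall-cohort result is judged against its Lan-DeMets final boundary at whichever Holm level applies, computed from the looks actually taken. For looks at 50% and 75% these are Z = 2.281 at step 1 (two-sided p about 0.0225) and Z = 2.014 at step 2 (about 0.044). Keep 0.025/0.05 for the nAb-negative test, which has no looks. Report the number and information times of the efficacy looks, or state that there were none, in which case E-4's thresholds stand.

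The cost is wording plus about one point of power for the overall hypothesis. At RRR 1.20 with 1,202 events, ln(1.20)·√1202/2 = 3.160, so power falls from Φ(3.160 − 1.960) = 88.5% to Φ(3.160 − 2.014) = 87.4%. For the first line of Table E-2 it falls from 0.899 to 0.889.

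### The AZD7442 power figures in Table E-4 are labelled as Holm power, but none is the power of the Holm rule in E-4; all are 0.1 to 0.9 points too high

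*SAP*

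**What the plan says.** E-4 of the SAP names two co-primary comparisons of AZD7442 with placebo for time to sustained recovery: the overall mITT cohort and its nAb-negative subgroup. On the error rate it says "The family-wise type 1 error rate will be controlled at the 0.05 (2-sided) level of significance", and on the method "The Holm method will be used to control the family-wise error rate". The rule is then spelled out: "The lower of the two p-values will be compared with a 0.025 (0.05/2) 2-sided level of significance". Only if that test is significant does the next step apply: "the second p-value will be compared with a 0.05 (2-sided) level of significance". Section 1.2 names the same method.

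The power inputs are in the same section: "Sustained recovery by Day 90 will be experienced by an estimated 545 participants in the nAb-negative subgroup"; "In the overall cohort, 1202 participants will achieve sustained recovery"; "48% of the study participants would be nAb-negative at study entry". The RRR is set at 1.32 in nAb-negative participants and varied from 1.30 to 0.95 in nAb-positive participants. The heading of Table E-4, its power columns and the text around Figure E-1 attribute the results to Holm's procedure. For an nAb-positive RRR of 1.0 the effect "would be detected with power of 0.858 in the nAb-negative subgroup, and with power of 0.63 in the overall study population". A comment rounds the first of these to 86%.

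**The concern.** Holm and Hochberg use the same two thresholds for two hypotheses and differ in one region only. If both p-values lie above 0.025 and at or below 0.05, Holm stops at its first step and rejects nothing, whereas Hochberg rejects both. With p = 0.03 and p = 0.04, for example, the rule in E-4 declares no success, while a Hochberg calculation counts two.

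If the printed powers include that region, they describe a more generous procedure than the one specified. At stake is the accuracy of the power stated for the primary analysis, and the risk that someone who checks or reuses the power calculation applies a different rule from the written one.

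**Working it through.** **Inputs from the SAP.** 545 events in the nAb-negative subgroup, 1202 overall, 48% nAb-negative, RRR 1.32 in nAb-negatives, two-sided family-wise 0.05 (all E-4); 1:1 allocation (section 1.3). Critical values are 1.9600 for two-sided 0.05 and 2.2414 for two-sided 0.025.

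**Inputs assumed.** The documents do not give the correlation of the two test statistics. Because the subgroup's events are a subset of the cohort's, I take sqrt(545/1202) = 0.673. I apply the 48% as a weight on the log RRR scale.

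**Step 1: reproduce the single-test power.** Mean of Z in nAb-negatives = ln(1.32) × sqrt(545)/2 = 0.2776 × 23.345/2 = 3.241. Power at 0.05 = Φ(3.2407 − 1.9600) = 0.900, as E-4 states.

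**Step 2: worked example, nAb-positive RRR 1.0.** Overall log RRR = 0.48 × ln(1.32) + 0.52 × ln(1.0) = 0.1333, so RRR = 1.14, as printed. Mean of Z overall = 0.1333 × sqrt(1202)/2 = 2.310.

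Holm rejects a hypothesis if its own p ≤ 0.025, or if its p ≤ 0.05 and the other p ≤ 0.025:
- nAb-negative: 0.8412 + 0.0102 = 0.8514
- overall: 0.5274 + 0.0960 = 0.6234

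Hochberg adds the probability that both p-values lie in (0.025, 0.05], here 0.0067:
- nAb-negative: 0.8514 + 0.0067 = 0.8581 (printed 0.858)
- overall: 0.6234 + 0.0067 = 0.6301 (printed 0.630)

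**Step 3: all rows** (nAb-negative / overall):

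| nAb-positive RRR | Printed | Hochberg | Holm |
|---|---|---|---|
| 1.30 | .900 / .994 | .8996 / .9937 | .8991 / .9932 |
| 1.25 | .899 / .985 | .8989 / .9850 | .8976 / .9837 |
| 1.20 | .897 / .967 | .8970 / .9672 | .8940 / .9642 |
| 1.15 | .892 / .933 | .8924 / .9331 | .8868 / .9275 |
| 1.10 | .884 / .873 | .8838 / .8726 | .8757 / .8645 |
| 1.05 | .871 / .774 | .8714 / .7737 | .8626 / .7650 |
| 1.00 | .858 / .630 | .8581 / .6301 | .8514 / .6234 |
| 0.95 | .848 / .453 | .8482 / .4526 | .8447 / .4491 |

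Hochberg matches 16 of 16 cells at three decimals and Holm none. Every printed value is above Holm, by 0.0008 to 0.0090, so rounding is not the cause.

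**Step 4: robustness.**
- Simulation with 4 million draws and two-sided rejection gives Holm 0.8518 / 0.6232 and Hochberg 0.8584 / 0.6299 at RRR 1.00. At 1.10 it gives Holm 0.8759 / 0.8646 and Hochberg 0.8840 / 0.8727.
- With correlation sqrt(0.48) instead, Hochberg is within 0.0007 of every cell and Holm still matches none.
- With correlation and weight left free, the best Holm fit found is off by up to 0.0028 and matches 2 of 16 cells. Freeing the overall event count as well gave 0.0031 and again 2 cells.
- Testing the second p-value at 0.05 whatever the first result gives 0.880 / 0.869 at RRR 1.10, against 0.884 / 0.873 printed.

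**The case against.** **The effect is small and nothing rests on it.** This stands. The largest gap is 0.9 points. The 1,228-event target was set in August 2021 (E-2), the last participant was randomized on 30 September 2021, and Table E-4 uses projections from 28 December 2021. No enrolment or sample-size decision could turn on it.

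**A reader might infer that the table is what justified the testing plan.** The documents do not say so. E-3 attributes the two-hypothesis plan to Tables E-2 and E-3, the fall in the nAb-negative share from 56% to 48%, and the relative importance of the two comparisons. Tables E-2 and E-3 are single-test calculations, which this point does not touch.

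**A reader might infer that the primary test is faulty, or should become Hochberg.** Neither follows. E-4 states Holm's rule completely, and Holm controls the family-wise error without any assumption about dependence. Hochberg would be defensible here because the nested tests are positively correlated, and it is never less powerful. But replacing a correctly pre-specified test, after pooled outcomes have been reviewed, so that a table can stand is the wrong way round.

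**That Hochberg was used is an inference.** This also stands. It rests on the 48% log-scale weighting and on an unstated correlation. If the log RRRs are weighted by events instead (545/1202 = 45.3%), overall power at nAb-positive RRR 1.00 is about 0.58 under either rule, against 0.630 printed, and neither rule fits the overall column. That choice is worth about 5 points, several times the Holm–Hochberg gap, which is a reason to state it.

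**Conclusion.** At the SAP's stated inputs and the nested correlation of 0.673, no cell of Table E-4 is the power of the Holm rule in E-4. The agreement with Hochberg in all 16 cells makes it likely, though not certain, that the power code counted the region with both p-values in (0.025, 0.05] as rejections. The printed power is too high by 0.1 to 0.9 percentage points. The worst case is the overall test at nAb-positive RRR 1.05, 0.774 printed against 0.765. This is a minor but reproducible error in a supporting table of the primary analysis. The decision rule, its error control, the sample size and the event target are unaffected.

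**What to change.** Keep the pre-specified Holm rule. Restate Table E-4 (nAb-negative / overall) by nAb-positive RRR:

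- 1.30: 0.899 / 0.993
- 1.25: 0.898 / 0.984
- 1.20: 0.894 / 0.964
- 1.15: 0.887 / 0.927
- 1.10: 0.876 / 0.864
- 1.05: 0.863 / 0.765
- 1.00: 0.851 / 0.623
- 0.95: 0.845 / 0.449

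Change the worked example to 0.851 and 0.623 and the comment from 86% to 85%, and redraw Figure E-1. Add one sentence giving the correlation between the two tests and the weighting used for the overall RRR. If the authors used other values for these, they should state them and recompute under Holm. The test itself and section E-5, which does not name Holm, need no change. The cost is a re-issued table and figure and a few lines of text, with no effect on data or participants.
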